11.2. Statistical and Analytical Plans

a. General Considerations

Independent t- tests will be used to compare both groups at 12 months post operation

“Success” will be defined as IOP unmedicated IOP</=21mmHg at 1 year and unmedicated IOP reduction of >/=20% at 1 year, with no additional anti-glaucomatous medications at 1 year. The rational for 20% reduction is based on published RCT trials that use 20% as a standard reduction expected from this device. The same reduction percentage is used for comparison to other published data.

Chi-square test will be used to compare success versus failure in both groups.

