3.3. Inclusion Criteria

Provide informed consent

Previous diagnosis of PAC or PACG

IOP above 21mmHg at 3 separate visits

On 1 or more hypotensive medications

Pre-operative VA of no better than 6/12

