4. TRIAL SCHEDULE

Part of research Schedule:

Patients who meet the inclusion criteria will be invited to participate in this study. Patient will be randomly assigned to either phacoemulsification alone, or phacoemulsification with iStent by random envelope shuffle technique.

After operation the patient will be followed up at day 1, week 1, week 2, months 1, 3, 6 and 12.

At each visit the patient will have the following tests: Tonometry (IOP check) - Not to be taken by the operating surgeon, to be taken by 2 people, one IOP checker and one reader.

Part of Standard of Care:

At each visit:

Visual Acuity, Slit lamp examination and Fundoscopy.

At 6 monthly intervals:

Visual field examination

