5. STUDY DESIGN

Single centre, randomised prospective trial, the patient and the IOP checking staff will be blinded. Randomised by random envelope shuffle technique.

1:1 ratio allocation

2 arms: phacoemulsification alone and phacoemulsification and iStent.

16 patients in each arm, 32 patients in total.

The post-operative management is the same for both arms

After operation the patient will be followed up at day 1, week 1, week 2, months 1, 3, 6 and 12.

At each visit the patient will have the following tests: Tonometry (IOP check) - Not to be taken by the operating surgeon, to be taken by 2 people, one IOP checker and one reader.

The target IOP is 18mmHg for patients with PAC or mild PACG. If the IOP rises above 18mmHg in 2 consecutive visits then the original glaucoma medication(s) will be reinstated or as per the clinicians discretion.

IOP at 12 months will be the primary outcome measure. The target pressure will be based on the Asia Pacific Glaucoma Guidelines. For PAC with high IOP and PAS and early PACG, the target will be $>/=20\%$ from base line or 18mmHg whichever is lower. b. The Asia Pacific Glaucoma Guidelines classifies “PAC with High IOP and PAS” to be “glaucoma with moderate 5-year risk for visual loss” and to treat the IOP with a target of $>/=20\%$ or 18mmHg whichever is lower.

The target IOP is 18mmHg for patients with PAC or mild PACG. If the IOP rises above 18mmHg in 2 consecutive visits then the original glaucoma medication(s) will be reinstated or as per the clinicians discretion.

The patient will be masked to the treatment arm given, but the investigators will not be masked.

The procedure will be performed by 2 surgeons: [name] and [name], the follow up visits and monitoring of pressure will be done by the investigation team.

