6.1. Randomisation and Blinding

This section should describe randomisation and blinding procedures (if applicable to the

study design). Include a description or a table that describes how study subjects will be assigned to the study groups. The timing and procedures for planned and unplanned breaking of randomization codes should be included. Include statement when unmasking may occur and who may unmask.

Randomised controlled study. 1:1 ratio allocation 32 patients 16 phacoemulsification alone 16 phacoemulsification with iStent Randomisation by shuffled envelope system.

Follow up will be at 1 day, 1 week, 1 month, 3 months, 6 months, 1 year after surgery.

Patient will be blinded to the procedure.

The IOP measure and reader will be blinded to the procedure.

There will be no planned breaking of randomisation.

Unplanned breaking will happen if any envelopes are damaged or lost.

Unmasking will take place after 1 year post operation by the study team to inform the patient of the procedure.

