6.3. Study Visits and Procedures

Provide a brief outline of the all the study visits, procedures to be done during the study, follow up after the study and discontinuation visit.

a. Screening Visits and Procedures

No formal screening visit.

The patient will be identified in clinic and be invited to participate in the trial.

b. Study Visits and Procedures

Patients who meet the inclusion criteria will be invited to participate in this study. Patient will be randomly assigned to either phacoemulsification alone or phacoemulsification with iStent by random envelope shuffle technique.

After operation the patient will be followed up at day 1, week 1, week 2, month 1, months 3, 6 and 12.

At each visit the patient will have the following tests: Tonometry (IOP check) - Not to be taken by the operating surgeon, to be taken by 2 people, one IOP checker and one reader.

c. Final Study Visit:

Final visit will be at 1 year after surgery.

Patient will be informed of the procedure performed.

They will resume normal follow up in the clinic for their glaucoma.

d. Post Study Follow up and Procedures

At each visit the patient will have the following tests: Tonometry (IOP check) - Not to be taken by the operating surgeon, to be taken by 2 people, one IOP checker and one reader.

As part of their routine assessment they will be examined for evidence of complications related to the operation.

e. Discontinuation Visit and Procedures

Subjects may withdraw voluntarily from participation in the study at any time.

They will be unmasked regarding the procedure performed. They will need to continue to have the same follow up schedule because it is the same standard of care, except that at each visit they will have tonometry taken by the same doctor (instead of a two person technique) in the clinic who will not be blinded to their operation status.

Subjects may also withdraw voluntarily from receiving the study intervention for any reason. If the patient does not have the operation, then they will receive the standard management for their condition which is usually 6 monthly follow up if their condition is stable.

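### Section 11.2 fixes an unadjusted t-test of 12-month IOP although every patient has pre-operative IOP; a pre-specified ANCOVA on baseline IOP would be a cheap improvement with a probably modest gain

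*Protocol*

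**What the plan says.** Protocol section 5 states: "IOP at 12 months will be the primary outcome measure". Section 2.3 also lists mean IOP at 1 year as a primary outcome. Section 11.2 then names the test: "Independent t- tests will be used to compare both groups at 12 months post operation". It mentions no covariate or baseline adjustment.

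Pre-operative IOP is nonetheless needed for every patient:

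- Entry under section 3.3 requires "IOP above 21mmHg at 3 separate visits".
- The target pressure in section 5 is set "from base line or 18mmHg whichever is lower".
- The success definition in section 11.2 needs a reduction of at least 20%, which cannot be computed without a starting value.

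Section 6.1 describes allocation as "Randomisation by shuffled envelope system", 1:1, 16 per arm, with no stratification.

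**The concern.** The named comparison discards a measurement that the trial must already hold. If pre-operative IOP predicts 12-month IOP, leaving it out has two costs.

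First, the variation it would explain stays in the error term, so the confidence interval is wider and average power lower than they need be. Second, with 16 per arm and no stratification, baseline IOP is balanced only by chance. Any imbalance carries through to the unadjusted difference, in either direction.

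Adjustment removes the linear part of an imbalance in measured baseline IOP. It does nothing directly about other factors such as number of medications, PAC versus PACG, or surgeon. It should be settled in advance, because adjustment chosen after an imbalance has been seen is open to the charge of selection.

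**Working it through.** **Inputs.** From section 11.1: difference 2.6 mmHg, alpha 0.05, power 0.80, SD 2.4, and source SDs 3.1 and 3.5. From section 5: 16 per arm. Pooled source SD = √((3.1² + 3.5²)/2) = 3.31. The correlation r is not in the protocol; 0 to 0.6 is assumed. Section 11.1 does not state sidedness; two-sided is used because it reproduces the plan's sample size.

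**The plan's own figure.** n per arm = 2(1.960 + 0.842)² × 2.4²/2.6² = 13.4, rounded up to 14, as stated. The one-sided equivalent gives 11. The sample size therefore rests on an unadjusted two-sided comparison.

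**Formulas at n = 16 per arm** (noncentral t):

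- t-test: SE = SD × √(2/16), 30 df.
- ANCOVA: SE = SD × √(1 − r²) × √(2/16) × √(1 + 1/28), 29 df. The last factor is the average cost of estimating the slope.

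**Average power and precision.**

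| | Power, SD 3.31 | Power, SD 2.4 | 95% CI half-width, SD 3.31 (mmHg) |
|---|---|---|---|
| t-test | 57.6% | 84.2% | 2.39 |
| ANCOVA, r 0 | 56.1% | 82.9% | 2.43 |
| r 0.2 | 57.8% | 84.4% | 2.38 |
| r 0.3 | 60.1% | 86.2% | 2.32 |
| r 0.4 | 63.5% | 88.8% | 2.23 |
| r 0.5 | 68.4% | 91.9% | 2.11 |
| r 0.6 | 75.2% | 95.3% | 1.95 |

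The break-even is r = 0.19 at both SDs. At SD 3.31, simulation gave 60.2% (r 0.3) and 68.4% (r 0.5) for ANCOVA, and 57.7% for the t-test.

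**Effect of the entry threshold.** Restricting entry to IOP above 21 mmHg narrows the baseline distribution and lowers r. As an illustration, cut a normal baseline at its mean. The variance ratio is v = 1 − 2/π = 0.363, and r′ = r√v / √(1 − r²(1 − v)).

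| Unrestricted r | r′ among those entered | Change in power, SD 3.31 | Change in power, SD 2.4 |
|---|---|---|---|
| 0 | 0 | −1.6 | −1.4 |
| 0.2 | 0.12 | −0.9 | −0.8 |
| 0.3 | 0.19 | −0.1 | −0.1 |
| 0.5 | 0.33 | +3.3 | +2.6 |
| 0.6 | 0.41 | +6.4 | +4.9 |

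On this model the unrestricted r must exceed about 0.31 to break even. The position of the cut is an assumption: with the baseline mean anywhere from 3 mmHg below it to 2 above, r 0.5 becomes 0.25 to 0.38.

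**Chance imbalance.** A baseline imbalance of exactly 1 SE shifts the unadjusted difference by r × SD × √(2/16). At SD 3.31 that is 0.35 mmHg (r 0.3) or 0.58 mmHg (r 0.5). In trials with that imbalance (200,000 simulated per cell), t-test power is 46% if it is adverse and 69% if favourable at r 0.3, and 37% and 78% at r 0.5. ANCOVA stays at 60% and 68% respectively in either direction.

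**The case against.** The strongest case against is that nothing here is wrong. The t-test is valid, it matches the unadjusted sample-size calculation, and covariate choice is often left to a statistical analysis plan. The first two points are true, and for that reason this is an improvement and not an error. The third does not dispose of it, because section 11.2 does name the test for the primary outcome; an analysis plan that used ANCOVA would depart from it.

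The second objection is that the benefit depends on an r the protocol does not give, and that r may be low. This stands. Besides the entry threshold, several features could weaken the correlation:

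- Patients enter "On 1 or more hypotensive medications".
- Medication may be reinstated after surgery (section 5).
- There is "No formal screening visit" (section 6.3), and the tonometry rule in section 4, "Not to be taken by the operating surgeon, to be taken by 2 people, one IOP checker and one reader", is specified only for post-operative visits.

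Over the whole assumed range, with the entry-threshold illustration applied, the change runs from about −1.6 to +6.4 points, so a small loss is possible.

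Third, the conditional power figures describe trials with an imbalance of exactly 1 SE. The t-test's average power and type I error already allow for chance imbalance, so those figures show the sensitivity of a single trial and are not an additional average loss.

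Fourth, the entry readings may mix medicated and unmedicated values of differing age. That can lower r, but any covariate measured before randomisation leaves ANCOVA valid.

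**Conclusion.** The concern holds as a recommended improvement. The named analysis is valid but leaves out a covariate that must exist for every patient. The likely gain in average power is about 0 to 6 points, the loss is about 1.5 points if r is 0, and the gain is larger (10.8 points at SD 3.31, 7.7 at SD 2.4) if r among enrolled patients reaches 0.5. The result would also depend less on chance imbalance in baseline IOP.

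These figures assume equal SDs, a common slope, a two-sided 5% test, no withdrawals, and values of r that the protocol does not supply. Confidence in the size of the gain is therefore only medium.

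Adjustment does not cure the conflict in section 11.1, where the SD of 2.4 is below both source SDs. For the residual SD to fall from 3.31 to 2.4, r would have to be √(1 − (2.4/3.31)²), about 0.69.

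**What to change.** In section 11.2, make the primary IOP comparison an ANCOVA of 12-month IOP on arm and baseline IOP, two-sided at 5%. Report the adjusted difference with its 95% CI, and keep the independent t-test as a sensitivity analysis.

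For this covariate only, define baseline in advance as the mean of the three qualifying pre-operative readings, recorded as values and not merely as an eligibility tick. It would help to note medication status at each reading.

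This definition should not set the baseline for the 20% success criterion. Readings selected for exceeding 21 mmHg would inflate a percentage reduction through regression to the mean, so that baseline needs its own definition.

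The cost is two sentences in section 11.2, recording of three values already obtained, and one degree of freedom. If r is 0, the price is 1.6 points of power at SD 3.31 or 1.4 at SD 2.4. No new visit is needed.

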1.2. Rationale and justification for the Study

The iStent has never been studied in primary angle closure or primary angle closure glaucoma. In Singapore or Chinese populations, primary angle closure and primary angle closure glaucoma is much more common than in the African and Caucasian populations. All iStent studies have been in patients with open angles, which is more common in the West. We have therefore selected this population for our study, which is more relevant in the Singapore context.

It is becoming more popular to remove the lens with phacoemulsification in angle closure glaucoma as a form of treatment to reduce IOP. It works by increasing the amount of space in the angle and the ultrasound component may also have an effect in increasing outflow. Interestingly, some patients also have an increase in IOP after surgery and some patients have no change in IOP after surgery.

The iStent is a FDA and HSA approved micro-bypass stent device that bypasses the trabecular meshwork (filtration membrane of the aqueous fluid exit pathway) and reroutes aqueous from the anterior chamber directly into canal of Schlemm and out of the eye. It lowers the IOP by increasing the outflow of fluid from the eye from the micro-bypass. In angle closure, the lens has to be removed to create enough space for the iStent to be inserted.

We therefore plan to compare the effects of phacoemulsification alone, to phacoemulsification with iStent implantation in patients with angle closure and angle closure glaucoma.

If the IOP can be better controlled with the phaco + iStent, then it can reduce the need for IOP lowering medications, and reduce the need for further invasive glaucoma surgery such as trabeculectomy, that have higher risks of adverse events.

We will perform a randomised controlled study, blinded to the patient and the IOP checking staff. Our hypothesis is that the phaco-iStent combined group will have a lower mean IOP at 1 year compared to the phacoemulsification alone group and that more patients will have an IOP of <21mmHg at 1 year in the combined phaco-iStent group, and the phaco-iStent group will require less medications at 1 year.

a. Rationale for the Study Purpose

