2.2. Primary Objectives

To assess the efficacy of the iStent trabecular micro-bypass stent (Glaukos Corporation, Laguna Hills, CA) in combination with cataract surgery in subjects with primary angle closure and mild to moderate primary angle closure glaucoma

2.3. Potential Risks and benefits:

a. End Points – Efficacy

The primary outcome is: unmedicated IOP \leq 21mmHg at 1 year and mean IOP at 1 year.

A secondary outcome measure is medication reduction at 1 year post operation

b. End Points - Safety

Safety measures include best corrected visual acuity, slit lamp observations, complications and adverse events

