3.5. Withdrawal Criteria

Complication during phacoemulsification including posterior capsular tear or vitreous loss.

Surgeon is unable to insert the iStent during surgery

Patient request to be withdrawn

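### The success rule in Section 11.2 fails an eye for added drops but not for further glaucoma surgery, so a drop-free eye after trabeculectomy can count as a success of its assigned operation

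*Protocol*

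**What the plan says.** Section 11.2 gives the success definition in full. The two pressure conditions read: success "will be defined as IOP unmedicated IOP</=21mmHg at 1 year and unmedicated IOP reduction of >/=20% at 1 year". The treatment condition follows: "with no additional anti-glaucomatous medications at 1 year". The definition feeds a planned test: "Chi-square test will be used to compare success versus failure in both groups".

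Other sections bear on later surgery:

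- **Section 1.2** expects better pressure control with the stent to "reduce the need for further invasive glaucoma surgery such as trabeculectomy, that have higher risks of adverse events".
- **Section 2.3, item a** gives the primary outcome as the proportion at or below the pressure limit without medication, together with the mean ("21mmHg at 1 year and mean IOP at 1 year"). It sets no condition on surgery.
- **Section 3.3** admits eyes with "IOP above 21mmHg at 3 separate visits" that are on at least one pressure-lowering drug.
- **Section 3.4** excludes earlier glaucoma surgery, but only at entry.
- **Section 3.5** lists intra-operative complications, patient request and "Surgeon is unable to insert the iStent during surgery" as grounds for withdrawal. Later glaucoma surgery is not among them.
- **Section 5** says that if pressure exceeds 18 mmHg at two visits in a row, "then the original glaucoma medication(s) will be reinstated or as per the clinicians discretion". It also says the investigators are not masked.

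**The concern.** The rule treats the milder rescue as failure and is silent on the stronger one. An eye still on added drops at 12 months fails. An eye whose assigned operation did so poorly that it needed a trabeculectomy can pass, because a working trabeculectomy is what would make it drop-free with a low pressure.

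This runs against the trial's own rationale, since the event the stent is meant to help avoid can be credited to the arm in which it occurred. If more control eyes are re-operated, the success comparison is biased against the stent. If problems with the stent lead to surgery, the comparison is biased in its favour. Because further treatment is partly at the discretion of unmasked investigators, the frequency could differ between arms for reasons other than the operations' effect.

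The scope is limited. Re-operated eyes that still need drops, or that miss a pressure condition, already count as failures.

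**Working it through.** **The plan's own figure.** The only stated calculation is the sample size in Section 11.1: difference 2.6 mmHg, SD 2.4 mmHg, alpha 0.05, power 0.80. Taken as two-sided, the normal approximation gives n = 2 × (1.960 + 0.842)² × 2.4² / 2.6² = 13.4, so 14 per arm, as stated. (The exact t-test gives 14.4, so 15.) This rests on mean IOP and does not use the success rule.

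**The rule applied to one eye.** Assume a baseline of 24 mmHg, a trabeculectomy during the year, and 14 mmHg without drops at 12 months.

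1. Pressure limit: 14 ≤ 21, met.
2. Reduction: (24 − 14)/24 = 41.7%, met. The 20% limit for this baseline is 0.8 × 24 = 19.2 mmHg.
3. No added drops at 12 months: met.

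The eye is a success under Section 11.2. None of Sections 2.3, 3.4, 3.5 and 5 reverses this.

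**Weight of one eye.** Sections 3.1 and 5 plan 16 patients per arm. One eye is 1/16 = 6.25 points and two are 2/16 = 12.5 points. The protocol gives no re-operation rate. Assuming 0 to 2 miscounted eyes per arm:

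- an arm's success rate is inflated by 0 to 12.5 points;
- the difference between arms shifts by -12.5 to +12.5 points;
- equal numbers in both arms leave the difference unchanged but inflate both rates.

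**Effect on the planned test.** The protocol gives no success rates either, so the counts below are assumed: 16 evaluated per arm, no dropout. The Pearson statistic is 32 × (ad − bc)² / (16 × 16 × total successes × total failures), where a and b are control successes and failures, and c and d are stent successes and failures.

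| Control v stent successes | Calculation | Chi-square | p, uncorrected | p, continuity-corrected |
|---|---|---|---|---|
| 7 v 13 | 32 × 96² / (256 × 20 × 12) | 4.80 | 0.028 | 0.068 |
| 8 v 13 | 32 × 80² / (256 × 21 × 11) | 3.46 | 0.063 | 0.137 |
| 7 v 12 | 32 × 80² / (256 × 19 × 13) | 3.24 | 0.072 | 0.150 |

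- If the true result is 7 v 13 and one re-operated control eye is counted as a success, it becomes 8 v 13: p goes from 0.028 to 0.063.
- If the true result is 7 v 12 and one re-operated stent eye is counted as a success, it becomes 7 v 13: p goes from 0.072 to 0.028.

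With continuity correction, the p-values move in the same directions, but none of the three falls below 0.05. Section 11.2 does not say which form of the test is meant.

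**The case against.** The strongest reply is that this is silence and not a wrong statement: nowhere does the protocol say that a re-operated eye is a success, and handling of rescue treatment is often settled in the SAP, which is not at hand. That would carry weight if Section 11.2 had left the definition open. It did not. It fixes a complete rule and makes one kind of rescue disqualifying, so applying the rule as written produces the wrong classification.

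The remaining points concern likelihood and size, and several of them stand:

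- **The route is narrow.** The population is angle closure and mild to moderate angle closure glaucoma, the named rescue is medication, and Section 1 places trabeculectomy after medication has failed. Within 12 months an eye would usually have to restart drops, fail on them, be operated on, recover and then be drop-free. Clinician discretion allows a shorter route but does not make it common. Zero affected eyes is plausible.
- **The trial is not sized on this variable.** Section 5 calls 12-month IOP the primary outcome measure and Section 11.1 sizes the trial on the mean. The composite in Section 11.2 also differs from the proportion named in Section 2.3.
- **The examples are constructed.** The counts are assumed, and crossing 0.05 depends on the uncorrected test.
- **The direction of bias is open.**
- **Such operations may be visible in the safety data.** Section 9.1 records adverse events, with action taken, throughout the year. That would help a reader find these eyes, but it would not make them efficacy failures.

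These points argue against treating the matter as critical. They do not remove the misclassification.

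**Conclusion.** The concern holds. As written, the rule in Section 11.2 counts an eye as a success of its assigned operation even if a later trabeculectomy produced the result, and no other section prevents this. The firm figure is 6.25 points per affected eye, given 16 evaluated per arm. The range of -12.5 to +12.5 points rests on an assumed 0 to 2 such eyes per arm, and the p-value examples rest on assumed success counts and the uncorrected test. If no eye is re-operated, nothing changes. The sample size is unaffected. The point should be corrected: the definition feeds a planned comparison, a single eye matters at this size, and settling the rule once re-operations are known would be a post hoc choice.

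**What to change.** Add to the success definition in Section 11.2: *and no further IOP-lowering surgery or laser to the study eye before the 12-month visit*. Report the number of such eyes by arm.

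The cost is one clause and one case report form item. Visits, treatment and sample size stay as they are, and the decision to offer surgery remains with the clinicians. The downside is slightly lower success rates if any eye is re-operated.
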